## **10.3 Respiratory Status**

Respiratory status data collected will be provided in a subject listing.

## **10.4 Vital Signs Measurements**

Vital signs measurement [body temperature (F), respiratory rate, radial pulse rate, systolic and diastolic blood pressure, and oxygen saturation (pulse oximetry will be summarized descriptively by treatment group for each study day collected. Additionally, the changes from baseline will be calculated and descriptive statistics presented.

## **10.5 Electrocardiogram (ECG) Results**

For each ECG parameter, descriptive statistics will be presented for each cohort by treatment group for values collected.

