## **7.0 GENERAL STATISTICAL CONSIDERATION AND DEFINITIONS**

### **7.1 Baseline and Visit Windows**

Unless otherwise specified, baseline, which is defined as the last non missing assessment prior to the first dose of the study treatment, will be used in baseline and change from baseline analyses. Analyses will be performed according to the scheduled visits.

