### **7.2 Summary Statistics**

Analysis will be summarized by treatment group of STI-5656 plus SOC or Placebo plus SOC, unless specified otherwise.

- Continuous endpoints will be summarized using descriptive statistics (number of participants, mean, standard deviation [SD], median, and maximum values) for each cohort. The summary statistic n will be the number of subjects with non-missing values. All means and medians will be reported to one more significant digit than the values being analyzed. Standard errors and standard deviations will be reported to two more significant digits than the values being analyzed. The minimum and maximum will be reported to the same number of significant digits as the values being analyzed.
- Categorical endpoints will be summarized as the number and percentage of participants per category for each cohort. Percentages will be out of the number of subjects in the population being reported, unless otherwise noted. All percentages will be rounded to one decimal point. The number and percentage of subjects will always be presented in the form XX (XX.X%) where the percentage is in parentheses. To ensure completeness, all summaries for categorical and discrete variables will include all categories, even if none of the subjects had a response in a particular category. Denominators for each analysis will be based on the population of interest (e.g., safety population; subjects with non-missing data).
- Subject listings of data will be presented for all enrolled subjects unless specified otherwise.

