## **10.2 Laboratory Results**

For each continuous laboratory parameter (chemistry, coagulation, hematology), descriptive statistics will be presented for each study day collected and for the changes from baseline for by treatment group.

Categorical urinalysis parameters will be presented as the number and percentage of subjects per category for each study day collected by treatment group.

For laboratory parameters with normal ranges, the shift from Baseline (low, normal, high) to each subsequent study day (low, normal, high) will be presented by treatment group.

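### SAP 10.5 summarises ECG values only as collected; within-subject QTcF change from baseline and by-arm counts of prolongation should be added

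*SAP*

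**What the plan says.** SAP 10.5 is one sentence: "For each ECG parameter, descriptive statistics will be presented for each cohort by treatment group for values collected". It does not name QTcF, change from baseline, thresholds or categories.

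The neighbouring sections plan more. For vital signs, SAP 10.4 says: "Additionally, the changes from baseline will be calculated and descriptive statistics presented". For continuous laboratory parameters, SAP 10.2 says "descriptive statistics will be presented for each study day collected and for the changes from baseline for by treatment group". Where normal ranges exist, it adds that "the shift from Baseline (low, normal, high) to each subsequent study day (low, normal, high) will be presented by treatment group".

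SAP 7.1 supplies a usable baseline: "baseline, which is defined as the last non missing assessment prior to the first dose of the study treatment". The same section says: "Analyses will be performed according to the scheduled visits". For continuous data SAP 7.2 lists "number of participants, mean, standard deviation [SD], median, and maximum values". On listings it says: "Subject listings of data will be presented for all enrolled subjects unless specified otherwise".

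Both schedules of assessments (footnote 7 in each) call for an ECG at screening, one between 2 and 4 hours after dosing, and others when clinically indicated. Protocol 8.2.2 places the timed ECG on Day 1. Protocol 5.2, criterion 5, excludes subjects with QTcF above 480 ms.

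**The concern.** Safety and tolerability is a stated secondary objective (SAP 2.1.2), and the eligibility limit shows that the sponsor treats QTcF as a risk criterion. A pre-dose and a timed post-dose ECG form a pair for each subject. The plan then summarises the two visits separately and gives up the pairing.

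Mean change is largely recoverable by subtracting the two visit means. Two things are not: the spread of individual changes, and a systematic by-arm count of subjects whose QTcF became long or rose sharply. A reader of the planned ECG table would see one maximum per visit and could not tell how many subjects lay near it or how far each had moved from baseline.

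**Working it through.** The plan gives no figure for ECG, so there is none to reproduce. The check has two parts.

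**1. Does another provision already order the analysis?**

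| Provision | What it gives | Does it close the gap? |
|---|---|---|
| SAP 7.1 | Defines a pre-dose baseline | No; it orders no ECG change analysis |
| SAP 7.2 | Statistics, formats and listings | No; it orders no ECG category or change |
| Protocol 9.4.4 | Change from Day 1 for continuous safety endpoints; number and percentage for categorical ones | No; see below |
| SAP 10.1 | AE tables by arm | In part; needs an investigator report. Protocol 10.3 sets AE criteria for laboratory values, with no ECG equivalent |
| Protocol 6.3 | Stopping rule | In part; needs a possibly related event of Grade 3 or higher |

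Protocol 9.4.4 comes closest and fails for three reasons. SAP 1.0 says its analyses supersede the protocol's high-level plan. The rule does not name ECG. And the scheduled Day 1 ECG is post-dose, so change from Day 1 would miss the pre-dose to post-dose contrast. (Footnote 1 of the schedules says generally that Day 1 assessments precede dosing. I take the specific ECG timing in footnote 7 and protocol 8.2.2 as governing.)

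**2. What do visit-level summaries leave undetermined?**

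Inputs: 40 per arm (SAP 5.0). Assumed, because the documents give none of them: SD 20 ms at both visits (range 15 to 25), mean 410 ms rising to 420 ms, normal changes, a 30 ms cut-off, and within-subject correlation r from 0.3 to 0.9.

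- SD of change = SD × √(2(1 − r))
- Expected count = 40 × P(Z > (30 − 10) / SD of change)

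| r | SD of change, ms (SD 20) | Expected count, SD 20 | SD 15 | SD 25 |
|---|---|---|---|---|
| 0.3 | 23.7 | 7.96 | 5.20 | 9.98 |
| 0.5 | 20.0 | 6.35 | 3.65 | 8.47 |
| 0.7 | 15.5 | 3.93 | 1.70 | 6.03 |
| 0.8 | 12.6 | 2.28 | 0.70 | 4.12 |
| 0.9 | 8.9 | 0.51 | 0.06 | 1.47 |

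Within each SD column the visit means and SDs are identical in every row. They do not determine the count.

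The precision of a between-arm difference is open in the same way. On post-dose values with SD 20, the 95% half-width is 1.96 × 20 × √(2/40) = 8.8 ms. On change it is that figure times √(2(1 − r)): 8.8 ms at r = 0.5 and 5.5 ms at r = 0.8. Below r = 0.5 change is the less precise measure. The visit summaries do not show which case applies.

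**The case against.** The strongest reply is that little is lost. The planned maximum shows whether anyone reached a long QTcF. Subject listings allow values above 480 ms to be counted, and changes derived, by hand. Test findings can be reported as AEs, which are tabulated by arm. No endpoint concerns QT. The categorical part is also partly a matter of preference: vital signs get no categories, and laboratory shifts apply only where normal ranges exist. All of this stands, and it is why the point is minor. It does not supply a prespecified by-arm summary of change.

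A reader might infer more from the table above: that two arms with equal visit summaries are likely to differ in how many subjects rise sharply. The documents do not support that. In randomised arms measured alike, the main route to such a difference is a drug effect that varies between subjects. If that effect is independent of baseline, it widens the post-dose SD, which SAP 10.5 does report. Take SD 20 and r = 0.8, and add an independent effect with SD 20. The SD of change goes from 12.6 to √(160 + 400) = 23.7 ms and the expected count from 2.3 to 8.0, but the post-dose SD goes from 20 to √(400 + 400) = 28.3 ms, visible in the planned table. Equal summaries with unequal counts need an effect negatively related to baseline. The illustration shows only that the spread of change is not determined.

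Two further limits stand. Neither document lists the ECG parameters recorded. Post-dose QTcF is inferred from the exclusion criterion and might have to be derived from QT and heart rate. And the only scheduled post-dose ECG follows the first dose, while dosing runs for up to 14 days.

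**Conclusion.** The point holds as a minor descriptive improvement. SAP 10.5 plans less for ECG than SAP 10.2 and 10.4 plan for laboratory tests and vital signs, gives no reason, and no other provision orders the missing summary. On the stated assumptions, what the visit summaries leave open at SD 20 is an expected count anywhere from 8.0 down to 0.5 of 40 subjects with a rise above 30 ms.

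It would be wrong to read this as a QT signal going undetected, or as a flaw in any efficacy analysis. Sample size, alpha and the primary endpoint are untouched, and the maximum, listings and AE tables give partial cover. The conclusion assumes that post-dose QTcF is recorded or derivable. It can describe only a first-dose effect, plus whatever clinically indicated ECGs add.

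Version limit: the SAP cites protocol V5.0, and the protocol supplied is V4.0. The core gap and the 2-4 h timing stand in the SAP itself. The eligibility limit, the placing of the timed ECG on Day 1, protocol 9.4.4, the AE criteria and the stopping rule are taken from V4.0.

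**What to change.** Amend SAP 10.5 before unblinding to add, by arm:

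- descriptive statistics of QTcF change from baseline, with baseline as the last pre-dose ECG under SAP 7.1;
- the number and percentage of subjects with any post-dose QTcF above 480 ms, the protocol's eligibility limit;
- the number and percentage with an increase from baseline above 30 ms and above 60 ms. These two cut-offs are assumptions, not taken from the documents, and should be fixed before unblinding.

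State that clinically indicated ECGs enter the counts. At present SAP 10.5 refers to all values collected while SAP 7.1 works by scheduled visit, so their place is unclear. If QTcF is not captured directly, say that it will be derived from QT and heart rate by Fridericia's formula. Note under the table that the scheduled post-dose ECG reflects the first dose only.

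The cost is one extra table from ECGs already scheduled. No new ECGs, subjects or alpha are needed.

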## **10.6 Physical Examination**

The results of the physical examination will be listed for each subject and study day collected.

## **10.7 Pregnancy Test for FCBP**

The results of the pregnancy test will be listed for each assessment visit day collected.

## **11.0 CHANGES TO THE PLANNED ANALYSES**

During the analysis and reporting process, any deviations from the statistical plan designed for this protocol will be described and justified in the clinical study report.

## 12.0 APPENDICES

### 12.1 Appendix 1: Schedule of Assessments

Assessments	Screening (Day -4 to -1)	Day 1 (Dose 1) 	Daily until hospital discharge	Hospital discharge or Early Term 	Outpatient visit: Day 28	Telephone Follow-up at Day 60 and 90
Informed Consent	X					
Assess eligibility	X	X				
Demographics 	X					
RT-PCR assay for SARS-CoV-2 	X					
Medical history (including COVID-19 history)	X					
Concomitant medications	X	X	X	X	X	
Physical exam, including weight; height 	X			X	X	
Vital signs 	X	X	X	X	X	
12-lead ECG (performed locally) 	X	X				
Pregnancy test for FCBP only 	X	X		X	X	
Urinalysis 	X	X	X		X	
Blood for hematology, coagulation and chemistry 	X	X	X	X	X	
Blood for CRP, serum ferritin, VEGF-A and cytokines  Day 3, 5, 7, 10, 14 and 28 only	X	X	X	X	X	
Respiratory Status 	X	X	X	X		
Adverse Events 	X	X	X	X	X	
Assess clinical status 	X	X	X	X		
IRT entry (at screening, randomization, then early termination or study completion)	X	X		X		X
Study Drug administration (QD p.o.)		X	X 			

---

CONFIDENTIAL

Assessments	Screening (Day -4 to -1)	Day 1 (Dose 1) 	Daily until hospital discharge	Hospital discharge or Early Term 	Outpatient visit: Day 28	Telephone Follow-up at Day 60 and 90
Sampling for pharmacokinetics 	X 	X 	X 			
Survival and additional experimental meds/ hospitalization/ICU status					X	X

Abbreviations: AEs: adverse events; ALC: Absolute lymphocyte count; ALT: alanine aminotransferase; AST: aspartate aminotransferase; CRP: C-reactive protein; BUN: blood urea nitrogen; CMP: complete metabolic panel; COVID-19: Coronavirus Disease 2019; D: day; ECG: electrocardiogram; ECMO: extracorporeal membrane oxygenation; ET: Early Termination; F: Fahrenheit; FCBP: female of childbearing potential; FiO2: Fraction of inspired oxygen; IRT: Interactive Response Technology; IL: Interleukin; IFN $\gamma$ : interferon gamma; QD: once daily; PaO2: partial pressure of oxygen in arterial blood; p.o.: by mouth; RBC: red blood cells; rbc/hpf: red blood cells per high power field; RRT: rapid response team; RT-PCR: Reverse transcription polymerase chain reaction; TNF $\alpha$ : tumor necrosis factor alpha; WBC: white blood cells

 All assessments on Day 1 are to be performed prior to first dose of STI-5656. Day 1 laboratory results do not need to be available prior to randomization (and first dose of STI-5656 if assigned to that arm) if lab results are available from the previous 24 hours

 If the subject wishes to discontinue from the study prior to Day 28 or hospital discharge, every effort should be made to perform an Early Termination (ET) Visit within 7 days after the decision to discontinue the study.

 Demographics includes age, sex, race, ethnicity, date of birth.

 SARS-CoV-24 positive RT-PCR test results received more than 7 days prior to planned randomization may be used to confirm eligibility if the site is unable to obtain a repeat sample and confirm results prior to planned randomization day and if the subject has progressive disease consistent with COVID-19.

 Height at screening only

 Vital signs include body temperature (F), respiratory rate, radial pulse rate, systolic and diastolic blood pressure, and oxygen saturation (pulse oximetry). Pulse and blood pressure should be taken with subject in at least in a semi-recumbent position. It is preferred to collect vital signs approximately mid-afternoon each day. Vital signs may be obtained at additional times as deemed necessary by the Investigator.

 ECG to be performed at Screening, between 2 and 4 hours after study drug dosing, and as clinically indicated.

 Females of childbearing potential must have a negative pregnancy test at screening and within 24 hours before randomization (Day 1) unless the previous negative pregnancy test was within 72 hours of Day 1. Urine pregnancy test is acceptable. The test should be repeated at the time of the Day 28 visit.

 Urinalysis performed locally. Urinalysis includes protein, glucose, and blood (microscopic) – red blood cells per high power field (rbc/hpf).

 Laboratory tests performed locally.

Hematology: Hemoglobin, hematocrit, red blood cell (RBC) count, RBC indices, mean corpuscular hemoglobin, mean corpuscular hemoglobin concentration, platelet count (or estimate), and white blood cell count including differential.

Coagulation: INR, PTT.

Chemistry: performed locally. 14-analyte complete metabolic panel (CMP): Albumin, alkaline phosphatase (ALP), alanine aminotransferase (ALT), aspartate aminotransferase (AST), bicarbonate, total bilirubin (TBIL), blood urea nitrogen (BUN), calcium, chloride, creatinine, glucose, potassium, sodium, total protein, D-dimer, fibrinogen.

 Cytokines include TNF $\alpha$ , IFN $\gamma$ , IL-6, IL-1 $\beta$ , IL-7, IL-8, IL-10, IL-12, IL-17, IL-18, IP 10, VEGF-A

 Record FiO2 (and PaO2) at the time of arterial blood gas sampling. If PaO2 is not available, use SpO2. Other respiratory status data to collect includes oxygen supplementation status: mechanical ventilation, face mask, nasal cannula or room air. Radiographic findings will also be collected.

 AEs will be collected from the time of informed consent to Day 60. Any ongoing AEs at Day 28 will be followed until resolution or stabilization.

 An 8-category ordinal scale of patient health status ranges: 0=no clinical or virological evidence of infection; 1=no limitation of activities; 2=limitation of activities; 3=hospitalized, no oxygen therapy; 4=oxygen by mask or nasal prongs; 5=non-invasive ventilation or high-flow oxygen; 6=intubation and mechanical ventilation; 7=ventilation + additional organ support – pressors, rapid response team (RRT), extracorporeal membrane oxygenation (ECMO); 8=death. See Section 18.2 for form.

 STI-5656 or placebo administration up to Day 14 or hospital discharge, whichever is sooner for subjects in Treatment Arm 1. Study drug capsules should be taken orally with 200-250 mL of water following at least 2 hours of fasting.

 Samples will be collected from the first 20 subjects enrolled. Sampling timepoints are as follows: Day 1 (predose) and at 0.5, 1, 2, 4, 8, 12, postdose on dosing days 1 and 8.

CONFIDENTIAL
